3.4. Dose Adjustment/Stopping Criteria

In the SAD part, a starting dose of 2.5 mg of IFB-088 administered as oral capsule was judged to be safe for a first-in-human administration. Escalation to the next higher dose and any dose

adjustments of the next dose levels will be based on safety and tolerability results and available PK data of the previously administered dose group.

In the tentative dosing scheduled, there will be a 2-fold increase from the first dose level (2.5 mg) to the second dose level. The dose levels of the following groups will be increased by 2-fold from the previous dose level, until the dose level of 40 mg, and then 1.5-fold between the 2 last dose levels. The planned dosing schedule may be adjusted to allow administration of intermediate doses.

In the MAD part, the planned doses are 15 mg per day (2 x 7.5 mg at 12-hour interval) in cohort 1, 30 mg per day (2 x 15 mg at 12-hour interval) in cohort 2 and 50 mg per day (2 x 25 mg at 12-hour interval) in cohort 3.

The decision to proceed to the next dose level of IFB-088, will be made by the Dose Escalation Committee based on safety, tolerability and preliminary PK data obtained at the prior dose level.

Dose escalation will stop at doses, which are predicted on the basis of ongoing PK projections, to correspond to concentrations greater than the PK stopping limits (Section 3.4.2).

3.4.1. *Data Package Requirements for Dose Escalation Committee Meetings*

Dataset from a dosing session including IFB-088 plasma concentrations from the previous dose(s)/cohort(s) and safety data including AEs, vital signs, ECG (12-lead) and laboratory parameters up to at least 32 hours post last dose will be available prior to dosing the next group.

The DEC, comprised of the Investigator, the Pharmacologist of the clinical center, the statistician, a representative of the Pharmacovigilance platform, and a Sponsor's representative, will be convened prior to the start of each subsequent dosing session to interpret the clinical safety, tolerability, laboratory data and PK exposure, and make a decision to proceed to the next higher dose. Additional advisors could be invited as required.

A DEC charter will be provided to the members before the start of the study.

The DEC may unblind the treatment assignment for any subject with an SAE or for any treatment group after reasonable justification (e.g. subjects experiencing grade 3 events or findings) (Sibille et al, 2010).

The DEC will make a recommendation to proceed to the next higher dose as per protocol, or to modify the next dose or to stop the trial.

At the end of each meeting, the DEC will document in writing the decision that has been taken.

3.4.2. *Dose Adjustment/Stopping Pharmacokinetic Criteria*

As pharmacokinetic is not linear in rats with significant differences between males and females, and is linear without sex differences in dogs, dog rather than rat data have been used to modelize human pharmacokinetics.

Dosing will be stopped if the observed AUC(0-inf), at a given dose level in **any** subject, is $> 111.14 \text{ ng/ml.h}^{-1}$ (simulated AUC for the highest efficient dose in Human, lower than the half AUC in dogs at the NOAEL) or if the observed C_{max} is $> 23.77 \text{ ng/ml}$ which corresponds to the half of the C_{max} at the NOAEL in dog.

If the predicted upper limit of 95% CI of AUC(0-inf) at the next dose level is $> 111.14 \text{ ng/ml.h}^{-1}$ or of Cmax is $> 23.77 \text{ ng/ml}$, the next dose level may be decreased, or a decision could be made not to dose further.

3.4.3. *Stopping Safety Criteria*

The dose should not be escalated further if one of the circumstances listed below occurs in subjects within the same cohort, unless it is obvious that the occurrence is not related to the administration of the treatment:

- Occurrence of a Serious Adverse Event considered at least possibly related to the IMP administration in one subject (See Section 8.3). In that case, study has to be immediately interrupted.
- Possibly drug related severe AE in 2 subjects in the same cohort, independent of within or not within the same system-organ-class (EMA Guidelines on strategies to identify and mitigate risks for first-in-human and early clinical trials with investigational medicinal products)
- Clinically significant drug-related laboratory abnormalities of the same character in 2 or more subjects e.g.
 - Alanine aminotransferase (ALT) or aspartate aminotransferase (AST) > 5 times the upper limit of normal (5 ULN) (Grade 3),
 - Creatinine $> 120 \mu\text{mol/L}$ (1.2 ULN) (Grade 1)(FDA's Guidance on Toxicity Grading Scale for Healthy Adult and Adolescent Volunteers Enrolled in Preventive Vaccine Clinical Trials; Sibille et al 2010).

Moreover, the occurrence of moderate adverse reactions within the same system-organ-class in more than one subject, and/or clinically significant changes from baseline measurements will be considered as a safety signal and will have to lead to increase caution and a closer assessment of safety parameters in the other subjects. In such a case, data from all subjects would be to be reviewed.

3.4.3.1. *Liver Chemistry Stopping Criteria*

Liver chemistry threshold stopping criteria have been designed to ensure subject safety and to evaluate liver event etiology (in alignment with the FDA premarketing clinical liver safety guidance).

Study treatment will be stopped **for a subject** if the following liver chemistry stopping criteria is met:

- ALT or AST $\geq 3\text{xULN}$

Refer to Section 8.10, Liver Chemistry Follow-up Procedures, for details of the required assessments if a subject meets the above criteria.

3.4.3.2. *Triglycerides Stopping Criteria*

Several subjects experienced hypertriglyceridemia during the SAD part of the study. All cases were below the threshold of 5.6 mmol/L (i.e. 5 g/L), above which hypertriglyceridemia is considered clinically significant (European Atherosclerosis Society, European Society of Cardiology, French Society of Endocrinology) and no correlation or possible dose relationship was established. Moreover, some subjects with hypertriglyceridemia were in the placebo groups.

Nevertheless, a stopping criterion for triglycerides has been added in the MAD part of the study:

Study treatment will be stopped for a subject if the following criterion is met:

- Serum triglycerides ≥ 5.6 mmol/L and the subject is receiving IFB-088

Study treatment will be stopped for the whole cohort and the dose will not be escalated, if the following criterion is met:

- Serum triglycerides ≥ 5.6 mmol/L in 2 subjects receiving IFB-088.

Next cohort could be administered a lower dose intermediate between the previous cohort and the present cohort.

3.4.3.3. *Renal disorders*

The dose should not be escalated further if one of the circumstances listed below occurs **in 2 or more subjects** within the same cohort:

- Creatinine > 120 $\mu\text{mol/L}$ (1.2 ULN) (Grade 1)
- Or a change from baseline ≥ 30 $\mu\text{mol/L}$ within 24 h
- Or a change from baseline $\geq 50\%$ within one week

(KDIGO definition Ostermann and Joannidis, 2016)

- Hematuria $> 2+$, verified by cytologic exam, on 2 samples and considered at least possibly related to the IMP
- Urinary ratio Beta 2 microglobulin/ creatinine $\geq 2\text{N}$

One subject that will meet one of these criteria above will be withdrawn from the study.

3.4.3.4. *QTc Withdrawal Criteria*

A subject that meets the criteria below will be withdrawn from the study. The QT correction formula used to determine discontinuation should be the same throughout the study.

- QTcB and QTcF > 500 msec, OR
- Change from baseline: QTc > 60 msec

Withdrawal decisions are to be based on an average QTc value of triplicate ECGs. If an ECG demonstrates a prolonged QT interval, obtain 2 more ECGs over a brief period, and then use the averaged QTc values of the 3 ECGs to determine whether the subject should be discontinued from the study.

The dose should not be escalated further if 2 or more subjects present a prolonged QT interval as defined above.

3.4.3.5. *Vital Sign Withdrawal Criteria*

The dose should not be escalated further if 2 or more subjects, within a dose-level, receiving IFB-088 experience a grade 3 vital signs (heart rate and/or blood pressure) adverse event that are deemed possible or probably related to study drug by the investigator.

The grading for adverse events is based on FDA's Guidance on Toxicity Grading Scale for Healthy Adult and Adolescent Volunteers Enrolled in Preventive Vaccine Clinical Trials:

Vital Signs*	Grade 3
Tachycardia (beats per minute)	> 130
Bradycardia - beats per minute**	< 45
Hypertension (systolic) - mm Hg	> 155
Hypertension (diastolic) – mm Hg	> 100
Hypotension (systolic) – mm Hg	< 80

*Assuming supine position, at least 5 min at rest conditions, not sleeping subjects, measurements on the same arm and several concordant results

**When resting heart rate is between 60-100 beats per minutes. Use clinical judgment when characterizing bradycardia among some healthy subject populations, for example, conditioned athletes.

Stopping rules for an individual subject, for the dose escalation and within a cohort are summarized in [Appendix 2](#).

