The dose of 2.5 mg per day was selected as the maximum recommended start dose for the present clinical trial, based on the following considerations:

1. According to the applicable guidelines on dose selection for first in human trials (paragraph 7.2 of EMEA/CHMP/SWP/28367/07 Rev. 1 and FDA guidance 2005 - Guidance for Industry Estimating the Maximum Safe Starting Dose in Initial Clinical Trials for Therapeutics in Adult Healthy Volunteers), the calculation of the maximum recommended start dose (MRSD) is based on the no observed adverse effect level (NOAEL) converted into a human equivalent dose (HED) from which a safety factor is applied to derive the MRSD. As suggested by the above guidelines, the rat species was selected, both in terms of toxicology (most sensitive species) and in terms of pharmacology (species used for some animal models).
2. The NOAEL in this species being 3mg/kg/day, the 6.2 division factor should be applied to convert animal dose to HED (FDA Guidance 2005), it translates into 0.484 mg/kg in humans, that corresponds to a daily dose of 29 mg for a human weighing 60 kg. A safety factor of 10 (FDA Guidance 2005) is then applied to calculate the **MRSD, which is thus estimated at 2.90 mg.**

1.2.2.3. *Determination of the maximal tested dose in human*

Assessment of the target dose based on efficacy data in rodents

IFB-088's biological target PPP1R15A is present only in defective cells. PPP1R15A protein being conformation sensitive and part of a protein complex, there is no validated *in vitro* assays available to evaluate IFB-088 efficacy. Therefore, the efficacy of IFB-088 was evaluated *in vivo* in different validated rodent models (transgenic mouse and rat models). A non-exhaustive list of animal efficacy studies is presented in Table 2.

Table 2: Summary of in vivo pharmacology studies for IFB-088 in several animal models

Therapeutic indication	Animal model (targeted organ)	Tested doses	Efficacy	Remarks
Charcot-Marie-Tooth-1A	PMP22 transgenic rat (Sciatic nerve tissue)	P.O.: 0.76 mg/kg SID	Very weak and partial	First partial effect observed Report CMT1A-REPORT-NC-2017-01
		P.O.: 2.29 mg/kg SID	Good	Report CMT1A-REPORT-NC-2017-01
Charcot-Marie-Tooth-1B	MPZ-S63del transgenic mouse (Sciatic nerve tissue)	P.O.: 1 mg/kg BID (2 mg/kg/day)	Good	Das et al. Science 2015
Amyotrophic Lateral Sclerosis	SOD1-G93A transgenic mouse (Brain tissue)	P.O.: 1 mg/kg BID (2 mg/kg/day)	Partial	Das et al. Science 2015
		P.O.: 5 mg/kg SID	Good	

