The maximum clinical dose was determined from dog data as the pharmacokinetic is not linear in rats with differences between sexes. Based on these elements and the Guidance for Industry M3(R2) FDA. The maximum clinical dose should not be higher than half of the AUC at the highest dose tested in dogs not showing toxicity (considered as NOAEL).

The mean AUC at the highest dose not showing toxicity in dogs (4.5mg/kg twice daily) is 376.46 ng/ml.h⁻¹ (Table 1). Therefore, half of the AUC is 188.23 ng/ml.h, which corresponds to a dose of 135.79 mg in a human being weighing 60kg.

According to the model, the corresponding AUC for a 60 mg daily dose in humans is 83.15 ng/ml.hr, which is far below 188.23 ng/ml.h (Table 5).

Data on C_{max} are consistent with those on AUC. The half of the C_{max} in dogs receiving 4.5 mg/kg twice daily is 23.77 ng/ml while the C_{max} in humans receiving a total daily dose of 60 mg is 10.57 ng/ml. Thus, the target dose of 60 mg/day (30 mg BID) can be considered as safe in humans.

Table 5: Predicted mean plasma Cmax and AUC(0-inf) in humans following first day dosing of IFB-088 and associated safety coverage

Daily dose (mg)	Daily administered doses (n x mg)	Escalating dose ratio	Expected Human Cmax (ng/ml)	Expected Human AUC (0-inf) (ng/ml.hr)	Cmax safety coverage % of corresponding maximal Cmax in human	AUC safety coverage % of AUC in dog
2.5	1 x 2.5		0.84	3.69	3.5%	0.98%
5	2 x 2.5	2	0.88	6.93	3.7%	1.84%
10	2 x 5	2	1.76	15.32	7.4%	4.07%
20	2 x 10	2	3.52	27.72	14.8%	7.36%
40	2 x 20	2	7.04	55.44	29.6%	14.73%
60	2 x 30	1.5	10.57	83.15	44.47%	22.09%

The escalating dose levels (Table 5) were chosen to not exceed an escalating ratio of 2 except for the last dose level with a smaller ratio of 1.5.

It might be worth noting that the antihypertensive drug Guanabenz, a structural analogue of IFB-088 (with only one atom difference), displays a similar biological activity on PPP1R15A (Tsaytler et al., Science 2011; Das et al., Science 2015) and similar pharmacokinetic profile in Sprague Dawley rats (plasma, brain, retina and sciatic nerve – Report 16-326). Guanabenz is still marketed in certain countries (including Japan) at doses up to 64 mg/day as 32mg/day BID.

Criteria to stop escalating dose:

The dose escalation will be stopped if in a given volunteer:

- The AUC is higher than 111.14 ng/ml.h (simulated AUC for the highest efficient dose in Human and which is lower than the half of AUC in dogs at the NOEL)

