- The C_{max} reaches 23.77 ng/ml.h (half of the C_{max} in dogs at the NOAEL).

The maximum recommended starting dose (MRSD) for IFB-088 in adult healthy volunteers was evaluated at 2.90 mg/day in Humans.

The maximal daily dose to be administered in Humans to cover the different envisioned therapeutic indications was evaluated at 80 mg/day. Therefore, in order ensure optimal safety, **the dose ranges selected are:**

- **2.5 mg/day for the first therapeutic dose;**
- **60 mg/day given as 2 administrations of 30 mg for the highest therapeutic dose.**

1.2.3. *Dose Rationale for the MAD part*

1.2.3.1. *Update on Safety coverage*

Additional toxicology studies have been conducted in rodent (rat) and non-rodent (dog) animal species to further assess IFB-088 safety (see sections 4.3.1 & 4.3.4 of Investigator's Brochure):

- GLP repeated dose toxicity studies in Sprague Dawley rats and Beagle dogs at doses up to 12 mg/kg/day for 13 weeks. Observations and pharmacokinetic parameters of IFB-088 and its major metabolite (IFB-139) are summarized in Table 6.

Table 6: Summary of results from the GLP 13-week toxicology studies in rats and dogs

Study	Regimen	Main findings	analyte	Day of admin.	sexe	Plasma Tmax	Cmax (ng/ml)	AUCt (ng/ml*h)
46232 TSR 13-week toxicology GLP study in Sprague Dawley Rats	Repeated administration 13 weeks P.O.: 1.5 mg/kg BID (6h between the 2 treatments) 3 mg/kg/day	NOAEL	IFB-088	1	Female	T1: 30min	1.69	8.07
					Male	T1: 30min	0.79	5.86
			IFB-088	90	Female	T1: 30min	1.63	8.86
					Male	T1: 10min	0.50	3.79
			Major metabolite IFB-139	1	Female	T1: 3h	1.20	7.85
					Male	T1: 7h	0.98	7.04
	Major metabolite IFB-139	90	Female	T1: 9h	0.93	9.43		
			Male	T1: 7h	1.56	8.98		
	Repeated administration 13 week P.O.: 3 mg/kg BID (6h between the 2 treatments) 6 mg/kg/day	At 6 mg/kg/day administered as 3 mg/kg BID for 13 weeks was considered as adverse due to: - 2 out of 10 males presented enlarged kidneys, with irregular colour and/or surface; these changes correlated with the presence of crystal nephropathy at microscopic examination. - One female presented non-adverse, reversible, minimal bile duct hyperplasia. There were no other remarkable, test item-related signs at 6 mg/kg/day	IFB-088	1	Female	T1: 30min	2.95	26.4
					Male	T1: 30min	2.01	13.4
			IFB-088	90	Female	T1: 30min	2.73	29.9
					Male	T1: 10min	2.94	23.6
			Major metabolite IFB-139	1	Female	T1: 7h	1.20	15.1
					Male	T1: 3h	4.67	36.6
	Major metabolite IFB-139	90	Female	T1: 9h	2.96	36.6		

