			Male	T1: 9h	13.7	99.1		
	Repeated administration 13 weeks P.O.: 6 mg/kg BID (6h between the 2 treatments) 12 mg/kg/day	12 mg/kg/day administered as 6 mg/kg BID for 13 weeks was considered as adverse due to: - crystal nephropathy in the kidneys was the main histopathological finding. This observation was adverse and not reversible after the 4-week treatment-free period. - In addition to deaths (males) and effects on body weight, the high-dose level of 12 mg/kg/day produced numerous other treatment-related findings, and it could be concluded that most of them were limited to this dose level. Most of the findings recorded at the high-dose were not reversible after a 4-week recovery period.	IFB-088	1	Female	T1: 30min	12.9	64.5
					Male	T1: 30min	5.50	58.0
IFB-088			90	Female	T1: 30min	9.42	72.5	
				Male	T1: 3h	5.90	113	
Major metabolite IFB-139			1	Female	T1: 30min	5.18	71.2	
				Male	T1: 3h	3.19	149	
Major metabolite IFB-139	90	Female	T1: 9h	9.92	123			
		Male	T1: 13h	35.3	628			
IFB088-13W-DOGS 13-week toxicology GLP study in Beagle Dogs	Repeated administration 13 weeks P.O.: 1.5 mg/kg BID (6h between the 2 treatments) 3 mg/kg/day	No adverse effect	IFB-088	1	Female	T1: 30min	9.3	102.7
					Male	T1: 30min	12.0	105.1
			IFB-088	90	Female	T1: 30min	13.4	78.8
					Male	T1: 30min	17.0	93.4
			Major metabolite IFB-139	1	Female	T1: 8h	1.20	10.0
					Male	T1: 3h	2.2	25.5
	Major metabolite IFB-139	90	Female	T1: 30min	3.7	20.9		
			Male	T1: 8h	3.1	28.8		
	Repeated administration 13 week P.O.: 3 mg/kg BID (6h between the 2 treatments) 6 mg/kg/day	No adverse effect	IFB-088	1	Female	T1: 3h	16.2	182.9
					Male	T1: 3h	17.4	188.8
			IFB-088	90	Female	T1: 3h	21.4	198.9
					Male	T1: 3h	20.0	197.4
			Major metabolite IFB-139	1	Female	T1: 8h	2.5	37.4
					Male	T1: 8h	4.6	56.5
	Major metabolite IFB-139	90	Female	T1: 6h	7.8	61.2		
			Male	T1: 12h	5.1	69.0		
	Repeated administration 13 weeks P.O.: 6 mg/kg BID (6h between the 2 treatments) 12 mg/kg/day	NOAEL	IFB-088	1	Female	T1: 3h	41.2	467.6
					Male	T1: 3h	51.2	650.0
IFB-088			90	Female	T1: 30min	84.8	517.0	
				Male	T1: na	78.6	759.8	
Major metabolite IFB-139			1	Female	T1: 8h	7.5	102.7	
				Male	T1: 8h	6.7	110.6	
Major metabolite IFB-139	90	Female	T1: 30min	21.8	158.6			
		Male	T1: 12h	20.9	225.4			

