In the 13-week GLP toxicity study in rats, the administration of IFB-088 at dose levels \geq 6 mg/kg/day (i.e. 3 mg/kg BID) led to adverse effects similar to those observed in the 28-day study, i.e. renal and haematology abnormal findings. **Thus, the NOAEL remained at 3 mg/kg/day, administered in one (studies 44289 TSR – 28-day treatment) or two doses in Sprague Dawley rats (studies 46232 TCR – 13-week treatment).**

In the 13-week GLP toxicity study in dogs (study IFB088-13W-DOGS), the administration of IFB-088 up to 12 mg/kg/day (i.e. 6 mg/kg BID) was well tolerated without any renal toxicity or other findings.

The NOAEL in Beagle dogs increased and was established at 12 mg/kg administrated in two doses (6 mg/kg BID).

After 13 weeks of IFB-088 treatment, the maximal exposures (AUC_t) at the NOAEL in Beagle Dogs were 517.0 and 759.8 ng/ml.h with C_{max} of 84.8 and 78.6 ng/ml in females and males respectively. At the NOAEL, IFB-139 the major metabolite has an AUC_t of 158.6 and 225.4 ng/ml.h with C_{max} of 21.8 and 20.9 ng/ml in females and males respectively (IFB-139 is an inactive metabolite).

1.2.3.2. *Determination of the maximal tested dose in the Multiple Ascending Dose part of the study*

This Phase 1 study was initially designed to support future clinical developments of IFB-088 in CMT and other degenerative pathologies, such as Multiple Sclerosis, Amyotrophic Lateral Sclerosis, Oculo-Pharyngeal Muscular Dystrophy and Retinitis Pigmentosa for which preclinical efficacy in animal models has been obtained.

Based on the extrapolation presented in paragraph 1.2.2.3, the maximal daily exposure to cover all targeted therapeutic indications was estimated at 111.14 ng/ml.h (simulated AUC in human for the highest efficient dose in animals). According to the interspecies population pharmacokinetics model, the simulated AUC_{0-24} for a 60 mg daily dose (2x30 mg/day) in humans was 83.15 ng/ml.h. Pharmacokinetic results of the SAD show an AUC_{0-24h} of 51.41 +/- 20.45 ng/ml.h, which is less than half of the maximal daily exposure expected to cover all targeted therapeutic indications (111.14 ng/ml.h). As initial targeted exposures will not be met in this study, the company made the strategic decision to focus only on the treatment of Charcot-Marie-Tooth disease, in which exposures required in animals for efficacy are lower.

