Based on results obtained in different CMT animal models, the exposure (AUC_{0-24h}) for optimal efficacy is estimated between 19.89 and 43.18 ng/ml.h and C_{max} for 2 administrations per day in the range of 2.5 to 3.89 ng/ml (Table 7). According to the pharmacokinetics results from the SAD in healthy volunteers, the three following doses of 15, 30 and 50 mg daily cover to the range of optimal efficacy (exposure between 12.82 and 42.62 ng/ml.h, C_{max} between 1.20 and 3.77 ng/ml). The escalating ratio is 2 between the low and middle doses and 1.66 between the middle and high doses. To conclude, the maximal ascending dose will be 50 mg daily (2 x 25 mg) according to the preclinical population pharmacokinetics model and the preliminary pharmacokinetics results of the single day.

Table 8: Predicted mean plasma C_{max} and $AUC(0-inf)$ in humans following 14-day dosing of IFB-088 and associated safety coverage

Daily dose (mg)	Daily administered doses (n x mg)	Escalating dose ratio	Expected Human C_{max} (ng/ml) ⁽¹⁾	Expected Human AUC (0-inf) (ng.hr/ml) ⁽¹⁾	C_{max} safety coverage % of C_{max} in dogs ⁽²⁾	AUC safety coverage % of AUC in dogs ⁽²⁾
15	2 x 7.5	-	1.20	12.82	1.5%	2.5%
30	2 x 15	2	2.26	25.57	2.9%	4.9%
50	2 x 25	1.67	3.77	42.62	4.9%	8.2%
Stopping criteria			23.77	111.14	30.2%	21.5%

(1) Data are extrapolated from pharmacokinetics results of the SAD observed at a daily dose of 60mg (30mg BID), taking into account that IFB-088 C_{max} and AUC are dose-proportional at these dose levels.

(2) Safety coverage is calculated based on C_{max} and AUC_t at NOAEL for the sex with the lowest C_{max} and the lowest AUC_t

Criteria for dose modifications or stopping dose escalation:

The criteria to modify planned doses or stop dose escalation will be the same as the ones used for single ascending dose escalation, as NOAEL in Sprague Dawley rats is maintained and NOAEL in Beagle dogs increased following the results of the 13-week GLP toxicity study, *i.e.*

- $AUC > 111.14$ ng/ml.h, and
- $C_{max} > 23.77$ ng/ml.

Based on the SAD exposure in humans and on the additional toxicity studies performed in animals, the daily doses for the multiple ascending dose to be administered in Humans to cover

the envisioned therapeutic indications (Charcot-Marie-Tooth) and to ensure maximum safety are:

- **15 mg/day given as 2 administrations of 7.5 mg in the first cohort;**
- **30 mg/day given as 2 administrations of 15 mg in the second cohort;**

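### The dog is the only toxicology species used to judge the MAD exposure limits and Table 8, yet expected exposure at 50 mg/day exceeds that at the rat twice-daily dose with crystal nephropathy, and no PK rule reacts

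*Combined protocol and SAP*

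**What the plan says.** **Species.** For the starting dose (section 1.2.2.2), "the rat species was selected, both in terms of toxicology (most sensitive species) and in terms of pharmacology". For the top dose (1.2.2.3), "The maximum clinical dose was determined from dog data as the pharmacokinetic is not linear in rats with differences between sexes". Section 3.4.2 repeats this for the PK stopping criteria: "dog rather than rat data have been used to modelize human pharmacokinetics".

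**Limits.** Escalation stops if any subject has AUC above 111.14 ng·h/ml or Cmax above 23.77 ng/ml (3.4.2, Appendix 2). The next dose may also be lowered if the predicted upper 95% limit passes either value. The AUC figure is the simulated human AUC at the highest efficient dose, derived from mouse efficacy; its stated safety check is that it lies below half the dog AUC at the NOAEL. The Cmax figure is half the dog Cmax at the NOAEL. For the MAD part (1.2.3.2), "The criteria to modify planned doses or stop dose escalation will be the same as the ones used for single ascending dose escalation", because the rat NOAEL was unchanged and the dog NOAEL rose. Table 8 expresses coverage as a percentage of dog NOAEL exposure only.

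**Rat findings.** In the 13-week study (Table 6), 3 mg/kg twice daily was judged adverse: "2 out of 10 males presented enlarged kidneys, with irregular colour and/or surface; these changes correlated with the presence of crystal nephropathy". At 6 mg/kg twice daily there were male deaths, and of the crystal nephropathy the table says: "This observation was adverse and not reversible after the 4-week treatment-free period".

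**Renal rules.** Section 3.4.3.3 stops escalation when two or more subjects in a cohort meet a renal criterion. For a single subject, "One subject that will meet one of these criteria above will be withdrawn from the study".

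**The concern.** Non-linear, sex-dependent rat kinetics are a good reason not to scale human kinetics from the rat. They are no reason to leave out the concentrations measured in rats at a dose with renal crystals, since comparing a measured rat AUC with an expected human AUC needs no scaling. The protocol itself calls the rat the most sensitive species. Section 1.3.2 supports twice-daily dosing by the 28-day dog study and does not discuss the 13-week rat study, which was also dosed twice daily and was adverse.

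At stake is what the dose escalation committee (DEC) sees when it decides on 50 mg/day in healthy men without medical benefit. Table 8 shows 8.2% of dog AUC, about a twelve-fold margin. No table sets human exposure beside rat exposure, where the comparison runs the other way.

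**Working it through.** **1. Reproduce Table 8 at 50 mg/day.** Coverage = expected human value / lower-sex dog value at the 13-week NOAEL (AUC 517.0, Cmax 78.6).
- AUC: 42.62 / 517.0 = 8.2%, as stated.
- Cmax: 3.77 / 78.6 = 4.8%, against 4.9% stated.
- Limits: 111.14 / 517.0 = 21.5% and 23.77 / 78.6 = 30.2%, both as stated.

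The AUC row implies 51.14 at 60 mg/day, not the reported SAD mean of 51.41; the latter would give 51.41 × 50/60 = 42.84. This does not matter below.

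**2. The same ratio against the rat at 3 mg/kg twice daily** (Table 6, IFB-088).

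| Rat group | AUC | 42.62 / AUC | Cmax | 3.77 / Cmax |
|---|---|---|---|---|
| Day 1 female | 26.4 | 1.61 | 2.95 | 1.28 |
| Day 1 male | 13.4 | 3.18 | 2.01 | 1.88 |
| Day 90 female | 29.9 | 1.43 | 2.73 | 1.38 |
| Day 90 male | 23.6 | 1.81 | 2.94 | 1.28 |

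Every ratio exceeds 1. At 30 mg/day (AUC 25.57) the Day 90 AUC ratios are 0.86 (female) and 1.08 (male).

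**3. Can the PK limits react?**
- Dose reaching the AUC limit, by proportion: 50 × 111.14 / 42.62 = 130 mg/day.
- Dose reaching the Cmax limit: 50 × 23.77 / 3.77 = 315 mg/day.
- Limits over Day 90 exposure at the adverse rat dose: AUC 111.14 / 29.9 = 3.7 and 111.14 / 23.6 = 4.7; Cmax 23.77 / 2.94 = 8.1 and 23.77 / 2.73 = 8.7.

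Assume lognormal AUC with the SAD coefficient of variation, 20.45 / 51.41 = 0.398. Then sigma = sqrt(ln(1 + 0.398²)) = 0.383 and mu = ln(42.62) − 0.383²/2 = 3.679.
- P(AUC > 111.14) = 0.0035 per subject; for any of six, 1 − (1 − 0.0035)^6 = 2%.
- P(AUC > 23.6, the Day 90 male rat value) = 0.91.
- Individual upper 95% bound: 76 (normal, 42.62 × (1 + 1.96 × 0.398)) to 84 (lognormal). The predicted-exposure rule would not trigger either.

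**4. Comparisons that point the other way.**
- 28-day rat study, adverse dose of 9 mg/kg once daily (Table 1): Cmax 20.58, 6.30, 10.38, 6.80, so 3.77 is 0.18 to 0.60 of these. AUC0-24 was 63.49, 38.66, 60.99, 65.79, so 42.62 is 0.67, 1.10, 0.70 and 0.65 of these, below three of four.
- Dose conversion (section 1.2.2.2: divide by 6.2, 60 kg): the NOAEL of 3 mg/kg/day converts to 29.0 mg, and 50 / 29.0 = 1.72. The adverse 6 mg/kg/day converts to 58.1 mg, and 50 / 58.1 = 0.86.

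**The case against.** Much can be said for the plan, and most of it limits how far the point reaches.

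- **Duration.** The rat finding is at 13 weeks and MAD dosing lasts 14 days. In the 10-day rat study, renal changes at 5 mg/kg once daily were judged non-adverse; that converts to 5 / 6.2 × 60 = 48 mg/day. This stands, as does the 28-day comparison above.
- **Cmax.** Section 1.2.2.1 credits lower Cmax for the better twice-daily tolerability. Rat Cmax also varies between studies: at 2.29 mg/kg, below the NOAEL, Table 3 gives 3.89 and 17.35 in males, both above 3.77. The Cmax ratios are therefore less robust than the AUC ratios.
- **Analyte.** The affected males had lower Day 90 parent AUC than females (23.6 against 29.9) but higher IFB-139 AUC (99.1 against 36.6). Section 1.3.2 reports IFB-088 in the crystals and the most intense IFB-139 signal there too. Parent exposure may not be the driver, so both analytes should be shown.
- **Dog and SAD data.** Dogs had no renal findings at AUC 517.0 to 759.8, and no renal signal is described after a single day at 60 mg.
- **Other protection.** Hydration, diuresis and beta-2 microglobulin monitoring are in place. Clinically significant changes prompt review of all subjects' data (3.4.3), and the DEC may modify the dose. A reader might infer that the two-subject renal rule alone guards the 50 mg/day decision; the documents do not support that.

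A reader might also infer that every limit comes from dog data. The AUC limit starts from mouse efficacy, the human model in 1.2.2.3 used rats and dogs, and the unchanged rat NOAEL is cited for keeping the limits. What holds is that the dog alone is used to judge whether these exposures are safe.

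**Conclusion.** The point holds in a limited form. Expected AUC and Cmax at 50 mg/day exceed every 13-week rat value at the adverse twice-daily dose (1.4 to 3.2 and 1.3 to 1.9 times). The coverage table omits this, the reason given does not justify the omission, and no PK rule in 3.4.2 responds to it. The ratios rest on Table 8's dose-proportional extrapolation from the SAD part and on comparing rat AUCt with human AUC(0-inf); the 2% figure also needs the lognormal assumption.

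A reader might conclude that 50 mg/day is unsafe or has no renal margin. The documents do not show that: the longer exposure, the 28-day comparison, the dose conversion and the dog data all leave it open. Nor can the 2 of 10 male rats be turned into a probability that human laboratory criteria are met in 14 days. The documents do not settle which species predicts human crystals, so the DEC should see both. This is a cheap improvement, not a reason to withhold the dose.

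**What to change.** 1. Add rat IFB-088 and IFB-139 exposure at 3 and 6 mg/kg/day to Table 8, and to the DEC report beside the observed human values.
2. For the 30 to 50 mg/day step, let one IFB-088 subject meeting any 3.4.3.3 criterion through Day 17 hold escalation until an unblinded DEC review decides to proceed, use an intermediate dose or stop. Keep the two-subject rule as the automatic stop. Name this trigger in 3.4.1 as a justified reason to unblind; a placebo allocation lifts the hold.

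**Cost.** No new samples or visits. The DEC already meets before each cohort, and Day 17 laboratory tests are scheduled, though the package would have to wait for them: the 3.4.1 minimum of 32 hours after the last dose ends earlier. The downside is a possible pause and some false alarms. The hold acts on 30 mg/day data and adds nothing for subjects already at 50 mg/day.

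**Not recommended.** Section 1.2.3.2 says "the company made the strategic decision to focus only on the treatment of Charcot-Marie-Tooth disease", so one might lower the AUC limit to the top of that target range, 43.18. Under the lognormal model above, P(AUC > 43.18) is about 0.06 at 30 mg/day and 0.41 at 50 mg/day. The any-subject rule would then stop about 31% and 96% of six-subject active groups.
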